13.6.4 Assessment of Causality to Study Procedure

The Investigator should use their clinical judgment as well as the guidelines in Table 5 to assess the relationship between study procedure and AE. Assessment of Causality to Study Procedure should include causality to such items as EGD with biopsy or blood draw (as appropriate), or other.

Table 5 Adverse Event Relationship to Study Procedure

Relationship to Study Procedure	Comment
Related	There is clear evidence that the event is related to a study procedure.
Possible	The event cannot be explained by the subject's medical condition, concomitant therapy, or other causes, and there is a plausible temporal relationship between the event and a study procedure.
Unlikely/Remote	An event for which an alternative explanation is more likely (e.g., concomitant medications or ongoing medical conditions) or the temporal relationship to any study procedure suggests that a causal relationship is unlikely (For reporting purposes, Unlikely/Remote will be grouped together with Not Related).
Not Related	The event can be readily explained by the subject's underlying medical condition, concomitant therapy, or other causes, and therefore, the Investigator believes no relationship exists between the event and a study procedure.

13.6.5 Action Taken

Action taken with respect to study drug will be categorized as none, study drug permanently discontinued, study drug temporarily withdrawn, or other (specify).

Action taken with respect to study participation will be categorized as none, withdrawal from study participation, or other (specify).

Action taken with respect to treatment of an AE will be categorized as none, concomitant medication, concomitant procedure, or other (specify).

13.6.6 Assessment of Outcome

Event outcome at resolution or time of last follow-up will be recorded as: recovered, recovering, not recovered, recovered with sequelae, fatal, or unknown.

13.7 Adverse Event Reporting Procedures

13.7.1 All Adverse Events

Any clinically significant AE that is ongoing at the time of study completion or ET will be followed by the Investigator until event resolution, the AE is otherwise explained, not considered clinically significant by the Investigator, or the patient is lost to follow-up.

All AE identified, whether serious or non-serious, will be recorded in the AE eCRF beginning after the time of first administration of study drug in the double-blind period of the study and ending at the time of study completion or ET of the double-blind period or the OLE period, whichever is later. Serious adverse events considered related to screening procedures will be recorded in the AE eCRF starting on the date of informed consent. Whenever appropriate, the CTCAE (version 5.0 or most current version) should be utilized for naming common AE ([Appendix 4](#)).

13.7.2 Serious Adverse Event Reporting

In the event of any SAE reported or observed during the study, whether or not attributable to the study drug, site personnel must report it immediately (**within 24 hours of becoming aware of the SAE**) by telephone or email to the Sponsor, Allakos Inc.

The SAE report forms will be provided to the investigational site to assist in collecting, organizing, and reporting SAE, and forms must be completed with as much information as is available and should be submitted to the Sponsor within 24 hours of becoming aware of the event. Serious adverse events must also be recorded on the AE eCRF and designated as “serious.”

Even when only minimal information is available for the initial SAE report, the Investigator should try to make a causality assessment, as the causality is used to determine the timing of regulatory reporting requirements. If the Investigator or designee is not available to sign the SAE report on initial submission, they should be contacted by telephone and their assessment documented on the SAE form (with a note stating signature is forthcoming). The Investigator **may change** their causality assessment based on follow-up information and submit an amended SAE report form.

All efforts will be made to obtain accurate and complete medical records for the SAE. All efforts to obtain information should be documented in the patient source documents.

The site will notify the IRB according to its guidelines.

The patient's condition will be followed by the Investigator or designated Subinvestigator until resolution of the condition or a return to baseline levels. If additional visits are required, the patient will be asked to return to the study site for further follow-up. If the condition is still ongoing at the time the patient exits the study, every effort will be made to continue to follow up with the patient for a reasonable period of time, as determined by the Investigator or until there is a return to baseline or stabilization of the condition. As additional information becomes available, such as hospital discharge notes and patient medical records, the Investigator will be notified and provided with all relevant information.

All SAE that have not resolved by the end of the study or that have not resolved on discontinuation of the patient's participation in the study must be followed until any of the following occurs:

- The event resolves.
- The event stabilizes.
- The event returns to baseline if a baseline value is available.
- The event can be attributed to agents other than the investigational product or to factors unrelated to study conduct.
- It becomes unlikely that any additional information can be obtained (patient or health care practitioner refusal to provide additional information, lost to follow-up after demonstration of due diligence with follow-up efforts).

Serious AE must be reported within 24 hours to:**SAE Reporting**

[contact]

Email: [contact]

13.7.3 Pregnancy Reporting

Pregnancies are captured if they occur in female patients or in the sexual partners of male patients from the time the patient is first exposed to the investigational product through Day 225 (± 3) or 84 (± 3) days after last dose if patient does not enroll in the OLE period of the study, or until the start of the first dose in the OLE period of the study, unless otherwise directed by Allakos.

Female patients must be instructed to discontinue all study drugs and inform the Investigator immediately if they become pregnant during the study. Male patients must be instructed to inform the Investigator immediately if their partner becomes pregnant during the study.

The Investigator must report any pregnancy to Allakos within 24 hours of becoming aware of it using the provided pregnancy reporting forms. Female patients must be immediately discontinued from study drug. An uncomplicated pregnancy will not be considered an AE or SAE, but all pregnancies in patients who received AK002 will be followed through term.

For male patients with female partners who become pregnant, the site will ask the father (the study subject) to provide information about the outcome of the pregnancy and information about the baby. If detailed health information about the mother is requested by Allakos, a Pregnant Partner Information Release Form will be provided to the site for the mother to sign.

Any congenital abnormalities noted at birth in the offspring of a patient who received AK002 will be reported as a SAE. If the patient received AK002, the outcome of any pregnancy and the presence or absence of any congenital abnormality will be recorded in the source documentation and reported to the Medical Monitor and Sponsor.

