7.4 Inclusion Criteria

Patients are eligible to enroll in the study if all of the following criteria are met:

- 1) Provide written informed consent.
- 2) Male or female aged ≥ 18 and ≤ 80 years at the time of signing the informed consent for entry.
- 3) Baseline endoscopic biopsy with ≥ 30 eosinophils/hpf in at least 3 hpf in the duodenum as determined by central histology assessment of biopsies collected during the screening EGD without any other significant cause for the eosinophilia.
- 4) Completion of at least 4 daily PRO questionnaires per week for a minimum of 3 weeks during screening.
- 5) A weekly average score of abdominal pain, nausea, or diarrhea ≥ 3 on the PRO questionnaire (score from 0–10) for at least 2 weeks of screening and a weekly average TSS of ≥ 10 for at least 2 weeks of screening.
- 6) Inadequate or loss of response to, or intolerant to standard therapies for EoD symptoms, which could include PPI, antihistamines, systemic or topical corticosteroids, and/or diet, among others.
- 7) If patient is on pre-existing dietary restrictions, willingness to maintain dietary restrictions throughout the study.
- 8) Willing and able to comply with all study procedures and visit schedule including follow-up visits.

9) Female patients must be either post-menopausal for at least 1 year with FSH level >30 MIU/mL at screening or surgically sterile (tubal ligation, partial or total hysterectomy, or bilateral oophorectomy) for at least 3 months or, if of childbearing potential, have a negative pregnancy test and agree to use dual methods of contraception, have a partner who had a vasectomy, or agree to abstain from sexual activity from screening until the end of the study, or for 120 days following last dose of study drug, whichever is longer.

Non-vasectomized male patients with female partners of childbearing potential must agree to either abstain from sexual activity or agree to use a highly effective method of contraception from screening until the end of the study or for 120 days following last dose of study drug, whichever is longer. All fertile men with female partners of childbearing potential should be instructed to contact the Investigator immediately if they suspect their partner might be pregnant (e.g., missed or later menstrual period) at any time during study participation.

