- 19) Vaccination with live attenuated vaccines within 30 days prior to initiation of treatment in the study, during the treatment period, or vaccination expected within 5 half-lives (4 months) of study drug administration. This exclusion criterion does not apply to all types and formulations of vaccines authorized by FDA or other regulatory authority for the prevention of COVID-19, which may be administered before, during, or after the study. The vaccine should not be administered within 7 days before and within 7 days after the administration of AK002 so that any side effects caused by either of the 2 medications can be more easily determined.
- 20) Participation in a concurrent interventional study with the last intervention occurring within 30 days prior to study drug administration (or 90 days or 5 half-lives, whichever is longer, for biologic products).
- 21) Known history of alcohol, drug, or other substance abuse or dependence that is considered by the Investigator to be ongoing and clinically significant.
- 22) Any other reason that in the opinion of the Investigator or the Medical Monitor makes the patient unsuitable for enrollment.

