11.5.1 Pregnancy Test and Follicle-Stimulating Hormone

A serum pregnancy (hCG) test will be completed for all female patients of childbearing potential. Women who are surgically sterile (tubal ligation, partial or total hysterectomy, or bilateral oophorectomy) for at least 3 months or those who are postmenopausal for at least 1 year with FSH level >30 MIU/mL are not considered to be of childbearing potential. At screening, FSH levels will be tested for female patients to confirm postmenopausal vs. childbearing status. Both FSH and hCG samples will be processed by the central laboratory.

Patients with FSH levels ≤ 30 MIU/mL are considered to be of childbearing potential. For patients of childbearing potential, the site will perform a urine dipstick pregnancy test prior to each study drug dosing and at Day 176 and Day 197 (± 3) or 35 (± 3) days and 56 (± 3) days after last dose of study drug if ET. This test is to be assessed by the study staff prior to the start of each study drug infusion. If a patient has a positive pregnancy test, dosing will immediately be discontinued.

To ensure patient safety, each pregnancy in a patient that received study drug must be reported within 24 hours of learning of its occurrence. If the patient received AK002, the pregnancy should be followed up to determine outcome, including spontaneous or voluntary termination, details of the birth, and the presence of absence of any birth defects, congenital abnormalities, or maternal and/or newborn complications. If the patient received AK002, any SAE experienced during pregnancy must be reported on the SAE Report Form.

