13.7.4 AESI Reporting

Beginning from the time of first study drug infusion in the double-blind period of the study and ending at the time of study completion or ET of the double-blind period or the OLE period, whichever is later, unless otherwise directed by Allakos, any new AESI or new information related to a previously reported AESI must be recorded in the AE eCRF and designated as an “AE of special interest.”

For patients participating in the OLE period, AESI will be assessed and recorded in the CRF of the AK002-021 double-blind treatment period database up until the start of the first open-label infusion after the Day 176 visit and recorded in the CRF of the AK002-021 OLE period database beginning from the start of the first open-label infusion after the Day 176 visit.

An AESI that also qualifies as a SAE (per Section 13.2) must also be reported as a SAE in accordance with Section 13.7.2. Adverse events of special interest that are also SAE must be recorded in the AE eCRF and designated as both “serious” and as an “AE of special interest.” These will be reported on the Sponsor-provided SAE forms and should be reported to the Sponsor within 24 hours of site awareness.

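### Pregnancy capture and follow-up stop 36 to 92 days before the protocol's 120-day contraception window closes

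*Protocol*

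**What the plan says.** Criterion 9 (Protocol 7.4, repeated in the synopsis) covers women who could conceive and non-vasectomized men whose partners could. They must abstain or use contraception from screening to the end of the study "or for 120 days following last dose of study drug, whichever is longer". Fertile men are also told to contact the investigator "if they suspect their partner might be pregnant (e.g., missed or later menstrual period) at any time during study participation".

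Section 13.7.3 sets a capture period for pregnancies in patients and partners. It opens at first exposure and closes at Day 225 (±3); its 84 (±3) day limit reads "days after last dose if patient does not enroll in the OLE period of the study, or until the start of the first dose", where the second limb concerns patients who enter the OLE. The sponsor may direct otherwise. The neighbouring rule for adverse events of special interest (AESI), 13.7.4, runs longer: "ending at the time of study completion or ET of the double-blind period or the OLE period, whichever is later".

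The duty to report rests on awareness and has no end date. Section 13.7.3 states: "The Investigator must report any pregnancy to Allakos within 24 hours of becoming aware of it using the provided pregnancy reporting forms". Section 11.5.1 says that "each pregnancy in a patient that received study drug must be reported within 24 hours of learning of its occurrence". What patients are told is narrower: "Male patients must be instructed to inform the Investigator immediately if their partner becomes pregnant during the study". The sentence for female patients in 13.7.3 has the same limit, the duration of the study.

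In the OLE (Appendix 13, Table 8), the last dose is on Day 316 and the last routine visit on Day 372. Early terminators have a visit 28 (±3) days after their last dose (note 21). Visits continue every 28 days only while lymphocyte or eosinophil counts have not recovered. They consist of a blood count and collection of AESI and serious adverse events (note 22).

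**The concern.** The protocol asks patients to avoid conception for at least 120 days after the last dose, but the stated stop rule and the visit schedule end before that. If contraception fails late in the window, nobody is scheduled to ask, and the patient's own instruction to report has lapsed with study participation.

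Exclusion criterion 19 shows that the interval is not arbitrary. It bars live vaccination "or vaccination expected within 5 half-lives (4 months) of study drug administration", so the protocol equates five half-lives with about the length of the contraception window. Followed as written, capture ends inside the sponsor's own precaution period. At stake is the completeness of a small body of safety information on exposed pregnancies. The co-primary and secondary analyses are not touched.

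**Working it through.** **Inputs.** Last double-blind dose: Day 141 (9.4). End of capture without OLE: Day 225, or 84 (±3) days after last dose (13.7.3). Last OLE dose: Day 316 (Table 8). Last routine OLE visit: Day 372, ±7 days in Table 8 and 19.13.1 but ±3 days in 14.1. OLE early-termination visit: 28 (±3) days after last dose (Table 8 note 21). Contraception window: at least 120 days (criterion 9).

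**The plan's own figures reproduce.** 225 − 141 = 84 days. 372 − 316 = 56 days, which is the 8 weeks in 19.13.1.

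**Part of the window without planned capture** (120 minus days covered):

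- Patients not entering the OLE: 120 − 84 = 36 days. With ±3 days: 120 − 87 = 33 to 120 − 81 = 39.
- OLE completers with recovered counts: 120 − 56 = 64 days. With ±7 days: 120 − 63 = 57 to 120 − 49 = 71. With ±3 days: 120 − 59 = 61 to 120 − 53 = 67.
- OLE early terminators with recovered counts: 120 − 28 = 92 days. With ±3 days: 120 − 31 = 89 to 120 − 25 = 95.

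**Testing ends earlier still.** The last scheduled double-blind pregnancy test is on Day 197, and 197 − 141 = 56 days after the last dose. OLE tests are predose only (Table 8 note 14), so the last falls on the day of the last dose.

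**Residual drug, as an indication only.** Assume first-order decline and a half-life of 4 months divided by 5: 120/5 = 24.0 days, or 122/5 = 24.4 days. The fraction remaining is 2^(−t/half-life):

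- Day 28: 0.445 to 0.451
- Day 56: 0.198 to 0.204
- Day 84: 0.088 to 0.092
- Day 120: 0.031 to 0.033

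**Where full capture would end.** 141 + 120 = Day 261 without the OLE; 316 + 120 = Day 436 after a full OLE course.

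**The case against.** The best defence is that a contraception window limits exposure while a capture window defines active surveillance, and the two need not be equal. The investigator must report any pregnancy on learning of it, with no end date, and the sponsor may extend capture. The consent and pregnancy forms, not available here, may tell patients what to do after the last visit. All this stands as mitigation. But the duty depends on someone telling the site, the sponsor's option is discretionary, and no contact is scheduled.

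The numbers are also small. The 84-day stop applies only to patients who stay out of the OLE. The synopsis says more than 90% of Phase 2 patients continued into the extension. If 80–90% did so here, 80 × 0.10 = 8 to 80 × 0.20 = 16 patients would be affected, roughly half of them on placebo. The continuation rate is an assumption. In the OLE, some patients would still be attending extended visits because counts had not recovered, and a pregnancy mentioned there would have to be reported. The documents give no recovery rate, and those visits do not list pregnancy.

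Three stronger readings are tempting, and the documents do not support them:

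- A reader might infer that the loss falls chiefly on partners, because 11.5.1 names only patients. But 13.7.3 limits the instruction to the duration of the study for both sexes, and its awareness duty covers any pregnancy.
- A reader might infer that no pregnancy is captured in the OLE, because 13.7.3 by its words stops at the first OLE dose and lacks the closing phrase of 13.7.4. Yet 19.13.5 runs the OLE under the protocol, including adverse event reporting, and a test precedes every dose. OLE dosing and follow-up are probably covered; the tail afterwards is not.
- A reader might infer that late pregnancies go unreported. They go unasked about; those that become known must be reported.

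**Conclusion.** The mismatch holds. Part of the minimum 120-day window has no planned pregnancy capture, for female patients and partners alike: about 36 days for patients who do not enter the OLE, 64 days for OLE completers and 92 days for OLE early terminators. The two OLE figures assume that blood counts have recovered, and the last takes note 21 as the only early-termination visit. The point does not rest on the half-life: the protocol never says that 120 days was derived from it, and the day counts alone show the shortfall.

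The number of pregnancies involved cannot be estimated. About 80 patients are randomized, and only some could conceive or father a child. This is a cheap improvement to safety surveillance and has no bearing on efficacy.

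**What to change.** Change 13.7.3 so that pregnancies in patients and partners are captured through 120 days after the last dose of study drug in the double-blind or the OLE period, whichever is later. Instruct female and male patients alike to report through that date, including after their last visit. A single telephone contact at day 120 is optional.

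Double-blind database lock follows completion of that period by all subjects (16.4). Capture to Day 261 inside the trial database could therefore hold the lock for up to 261 − 225 = 36 days after the last non-OLE patient's final visit. Record pregnancies arising after the last visit on the pregnancy forms in the safety database, outside the lock.

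The cost is an amendment with ethics approval (17.1), slightly longer passive safety follow-up and, if used, one call per patient. Visits, procedures, dosing and analyses stay as they are.

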13.7.4 AESI Reporting

Beginning from the time of first study drug infusion in the double-blind period of the study and ending at the time of study completion or ET of the double-blind period or the OLE period, whichever is later, unless otherwise directed by Allakos, any new AESI or new information related to a previously reported AESI must be recorded in the AE eCRF and designated as an “AE of special interest.”

For patients participating in the OLE period, AESI will be assessed and recorded in the CRF of the AK002-021 double-blind treatment period database up until the start of the first open-label infusion after the Day 176 visit and recorded in the CRF of the AK002-021 OLE period database beginning from the start of the first open-label infusion after the Day 176 visit.

An AESI that also qualifies as a SAE (per Section 13.2) must also be reported as a SAE in accordance with Section 13.7.2. Adverse events of special interest that are also SAE must be recorded in the AE eCRF and designated as both “serious” and as an “AE of special interest.” These will be reported on the Sponsor-provided SAE forms and should be reported to the Sponsor within 24 hours of site awareness.

13.9 Independent Data Monitoring Committee

An Independent Data Monitoring Committee (iDMC) has been convened for this study. The iDMC will meet at established intervals (as per the iDMC Charter) throughout the study and will also convene as necessitated by data and/or safety reviews.

13.10 Study Withdrawal Criteria

Participation of a patient will be discontinued in the event that:

- Occurrence of an exclusion criterion, which is clinically relevant and affects the patient’s safety, if discontinuation is considered necessary by the Investigator and/or Sponsor.
- Rebounding of eosinophil counts to $>1500/\mu\text{L}$ in patients who entered the study with eosinophil levels $>1500/\mu\text{L}$, and whose eosinophil counts were initially suppressed after study drug will be withdrawn from the study at the instruction of the Safety Monitor.
- Serum transaminases (ALT and/or AST) $>3 \times \text{ULN}$ and total bilirubin $>2 \times \text{ULN}$ (confirmed by subsequent repeat) without an alternative explanation.
- Elevation of ALT or AST $>3 \times \text{ULN}$ (confirmed by repeat) with the appearance or worsening of symptoms felt by the Investigator to be potentially related to hepatic inflammation, such as fatigue, nausea, vomiting, right upper quadrant pain or tenderness, fever, rash.

